CLINICAL STUDY PROTOCOL

PROSPECTIVE, DOUBLE-BLIND, RANDOMIZED, PLACEBO-CONTROLLED PHASE III STUDY EVALUATING EFFICACY AND SAFETY OF OCTAGAM 10% IN PATIENTS WITH DERMATOMYOSITIS

(ProDERM Study)

Investigational Product:	Immune Globulin Intravenous, Human 10% (Octagam 10%)
Indication:	Dermatomyositis (DM)
Study Design:	Prospective, parallel group, double-blind, randomized, placebo-controlled, multicenter, phase III study.
Sponsor:	Octapharma Pharmazeutika Produktionsges.m.b.H. [name]
Study Number:	GAM10-08
EudraCT and IND Number:	EudraCT 2016-002902-37 / IND 16925
Development Phase:	Phase III
Planned Clinical Start:	Quarter 4 2016
Planned Clinical End:	Quarter 4 2019
Date of Protocol:	18-Jun-2019
Version:	12
Coordinating Investigator:	Phoenix Neurological Associates [name]

This document contains confidential and proprietary information of Octapharma. Copying or distribution of this document is only permitted with the written permission of Octapharma. Any commercial use of the information is subject to the permission of Octapharma and a license fee.

This document contains confidential and proprietary information of Octapharma Pharmazeutika Produktionsges.m.b.H.

Do not copy or distribute without written permission.

STUDY OUTLINE

Name of Sponsor/Company: Octapharma Pharmazeutika Produktionsges.m.b.H., [name]				
Name of Investigational Product:	Protocol Identification Code:			
Octagam 10%	GAM10-08 (ProDERM), Version 12			
Name of Active Ingredient:	Date of Protocol:			
Immune Globulin Intravenous, Human 10%	18-Jun-2019			

Title of Study:

Prospective, Double-blind, Randomized, Placebo-Controlled Phase III Study Evaluating Efficacy and Safety of Octagam 10% in Patients With Dermatomyositis ("ProDERM study")

Indication:

Dermatomyositis (DM).

Number of Study Centre(s):

Approximately 55 selected study sites worldwide.

Objectives:

Primary Objective:

The primary objective of this study is to provide confirmatory data on the beneficial effect of 2.0 g/kg of Octagam 10% given every 4 weeks compared with placebo in subjects with active DM based on the percentage of responders at Week 16.

Secondary Objectives:

The secondary objectives of this study are

- to evaluate the beneficial effect of Octagam 10% in subjects with active DM by assessing different parameters and scores at Week 16 and Week 40;
- to confirm the sustained benefit of treatment with Octagam 10% by assessing the primary response measures at Week 40;
- to evaluate the safety and tolerability of Octagam 10% in subjects with DM.

Study Design:

Prospective, parallel group, double-blind, randomized, placebo-controlled, multicenter Phase III study with a controlled 16-week efficacy period followed by a 24-week openlabel extension period.

Number of Subjects:

A minimum of 94 adult subjects of both genders are to be enrolled.

Name of Sponsor/Company: Octapharma Pharmazeutika Produktionsges.m.b.H., [name]			
Name of Investigational Product:	Protocol Identification Code:		
Octagam 10%	GAM10-08 (ProDERM), Version 12		
Name of Active Ingredient:	Date of Protocol:		
Immune Globulin Intravenous, Human 10%	18-Jun-2019		

Subject Selection Criteria:

Inclusion Criteria:

- 1. Subjects with diagnosis of definite or probable DM according to the Bohan and Peter criteria.
- Subjects under treatment with corticosteroids and/or maximally 2 immunesuppressants and being on stable therapy for at least 4 weeks (see Section 4.2.1) OR
 - Subjects with previous failure of response or previous intolerance to corticosteroid and at least 1 additional immunosuppressive drug, and with steroid/immunosuppressive drugs washed out as per Section 4.2.1 (Table 2).
- 3. Subjects with active disease, assessed and agreed upon by an independent adjudication committee.
- 4. Manual Muscle Testing-8 (MMT-8) score <142, with at least 2 other abnormal Core Set Measures (CSM) (Visual Analogue Scale [VAS] of patient global activity ≥2 cm, physician's global disease activity ≥2 cm, extra-muscular activity ≥2 cm; at least one muscle enzyme >1.5 times upper limit of normal, Health Assessment Questionnaire ≥0.25).
- 5. Males or females ≥ 18 to ≤ 80 years of age.
- 6. Voluntarily given, fully informed written consent obtained from subject before any study-related procedures are conducted.
- 7. Subject must be capable to understand and comply with the relevant aspects of the study protocol.

Exclusion Criteria:

- 1. Cancer-associated myositis, defined as the diagnosis of myositis within 2 years of the diagnosis of cancer (except basal or squamous cell skin cancer or carcinoma in situ of the cervix that has been excised and cured and at least 1 or 5 years, respectively, have passed since excision).
- 2. Evidence of active malignant disease or malignancies diagnosed within the previous 5 years (including hematological malignancies and solid tumors) or breast cancer diagnosed within the previous 10 years.
- 3. Subjects with overlap myositis (except for overlap with Sjögren's syndrome), connective tissue disease associated DM, inclusion body myositis, polymyositis, juvenile dermatomyositis or drug-induced myopathy.
- 4. Subjects with immune-mediated necrotizing myopathy with absence of typical DM rash.

Name of Sponsor/Company: Octapharma Pharmazeutika Produktionsges.m.b.H., [name]			
Name of Investigational Product:	Protocol Identification Code:		
Octagam 10%	GAM10-08 (ProDERM), Version 12		
Name of Active Ingredient:	Date of Protocol:		
Immune Globulin Intravenous, Human 10%	18-Jun-2019		

- 5. Subjects with generalized, severe musculoskeletal conditions other than DM that prevent a sufficient assessment of the subject by the physician.
- 6. Subjects who have received IgG treatment within the last 6 months before enrolment.
- 7. Subjects who received blood or plasma-derived products (other than IgG) or plasma exchange within the last 3 months before enrolment.
- 8. Subjects starting or planning to start a physical therapy—directed exercise regimen during the trial.
- Cardiac insufficiency (New York Heart Association III/IV), cardiomyopathy, significant cardiac dysrhythmia requiring treatment, unstable or advanced ischemic heart disease.
- 10. Severe liver disease, with signs of ascites and hepatic encephalopathy.
- 11. Severe kidney disease (as defined by estimated glomerular filtration rate (eGFR) < 30 mL/min/1.73 m²).
- 12. Known hepatitis B, hepatitis C or HIV infection.
- 13. Subjects with a history of TEE such as deep vein thrombosis, pulmonary embolism, myocardial infarction, ischemic stroke, transient ischemic attack, peripheral artery disease (Fontaine IV) ever.
- 14. Body mass index \geq 40 kg/m².
- 15. Medical conditions whose symptoms and effects could alter protein catabolism and/or IgG utilization (e.g. protein-losing enteropathies, nephrotic syndrome).
- 16. Known IgA deficiency with antibodies to IgA.
- 17. History of hypersensitivity, anaphylaxis or severe systemic response to immunoglobulin, blood or plasma derived products or any component of Octagam 10%.
- 18. Known blood hyperviscosity, or other hypercoagulable states.
- 19. Subjects with a history of drug abuse within the past 5 years prior to study enrollment.
- 20. Subjects unable or unwilling to understand or comply with the study protocol.
- 21. Participating in another interventional clinical study with investigational treatment within 3 months prior to study enrollment.
- 22. Women who are breast feeding, pregnant, or planning to become pregnant, or are unwilling to apply an effective birth control method (such as implants, injectables, combined oral contraceptives, some intrauterine devices [IUDs], sexual abstinence or vasectomized partner) up to four weeks after the last IMP infusion.
- 23. Subjects who are accommodated in an institution or care facility based on an official directive or court order.

Name of Sponsor/Company: Octapharma Pharmazeutika Produktionsges.m.b.H., [name]			
Name of Investigational Product:	Protocol Identification Code:		
Octagam 10%	GAM10-08 (ProDERM), Version 12		
Name of Active Ingredient:	Date of Protocol:		
Immune Globulin Intravenous, Human 10%	18-Jun-2019		

- 24. Subjects who are in any way dependent on the Sponsor, Investigator or Study Site.
- 25. Subjects who received forbidden medication within the washout period as defined in Section 4.2.2 (Table 3).

Test Product, Dose, and Mode of Administration:

Octagam 10% is an IGIV ready for intravenous administration. The product is delivered as ready-to-use solution in glass bottles. Octagam 10% should be stored and transported light-protected at +2°C to +8°C (36°F to 46°F) and must not be frozen.

First Period (Octagam 10% vs. placebo in double-blind design): 2.0 g/kg (20 mL/kg) Octagam 10% or 20 mL/kg placebo given over 2 to 5 days at 4-week intervals (in total 4 infusion cycles).

Extension Period: 2.0 g/kg (20 mL/kg) Octagam 10% given over 2 to 5 days at 4-week intervals (in total 6 infusion cycles). At Week 28, subjects who are stable on 2.0 g/kg Octagam 10% can be switched to 1.0 g/kg (10 mL/kg) Octagam 10%, at the discretion of the investigator.

Duration of Treatment:

The duration of the entire study for each subject will be up to 43 weeks and consists of the following segments: up to 3 weeks for Screening, then 16 weeks of double-blind treatment phase (First Period) followed by 24 weeks of open-label treatment (Extension Period).

Reference Therapy, Dose, Mode of Administration:

Sodium chloride 0.9% w/v solution.

Study Outcome Parameters (Primary and Secondary Endpoints):

Efficacy Endpoints:

Primary

 Proportion of responders in the 2.0 g/kg Octagam 10% and placebo arms at Week 16. A responder is defined as a subject with an increase from baseline (Week 0) of ≥20 points on the Total Improvement Score (TIS) and who has not met "Confirmed Deterioration" criteria at 2 consecutive visits as defined in Section 4.3.1 up to (including) Week 16.

Secondary

- Proportion of TIS responders by improvement category (minimal, moderate, major) at Week 16 and Week 40.
- Mean change from baseline (Week 0) to end of First Period (Week 16) in the modified Cutaneous Dermatomyositis Disease Area and Severity Index (CDASI).

Name of Sponsor/Company: Octapharma Pharmazeutika Produktionsges.m.b	b.H., [name]
Name of Investigational Product:	Protocol Identification Code:
Octagam 10%	GAM10-08 (ProDERM), Version 12
Name of Active Ingredient:	Date of Protocol:
Immune Globulin Intravenous, Human 10%	18-Jun-2019

- Mean change from end of First Period (Week 16) to end of Extension Period (Week 40) in the modified CDASI.
- Mean change from Baseline (Week 0) to end of First Period (Week 16) and Extension Period (Week 40) in:
 - o SF-36v2 Health Survey;
 - o Individual 6 CSM used for TIS calculation.
- Mean TIS from Baseline (Week 0) to end of First Period (Week 16) and from Baseline (Week 0) to end of Extension Period (Week 40).
- Time to minimal, moderate and major improvement in TIS.
- Time to confirmed deterioration in the First Period and overall.
- Proportion of subjects in each treatment arm who met confirmed deterioration criteria up to (including) Week 16

Safety Endpoints:

Safety (throughout the entire First and Extension Period):

- Occurrence of all adverse events with particular emphasis on thromboembolic events (TEEs) and hemolytic transfusion reactions (HTRs).
- Occurrence of all adverse drug reactions (ADRs) and suspected ADRs.
- Vital signs (blood pressure, heart rate, body temperature and respiratory rate).
- Physical examination (at Screening and every 12 weeks from Week 4 on).
- Laboratory parameters (hematology, clinical chemistry).

Safety (at Baseline and end of Extension Period):

- Tests for viral safety.
- Pregnancy test, if applicable.

Study Procedures:

Subjects eligible after screening will be randomized 1:1 to receiving up to 4 infusion cycles of either Octagam 10% or placebo every 4 weeks during the First Period lasting 16 weeks. After response assessment at Week 16, all subjects who have not deteriorated at 2 consecutive visits during the First Period will continue to receive 2.0 g/kg (20 mL/kg) of Octagam 10% during the subsequent 6-months Extension Period. At Week 28, the subject may be switched to 1.0 g/kg (10 mL/kg) Octagam 10%, if previously has been stable on the 2.0 g/kg (20 mL/kg) Octagam 10% dose.

In case of confirmed deterioration (i.e. deterioration at 2 consecutive visits) during the First Period, subjects will be switched to the alternate treatment. After response assessment at Week 16 this subgroup of subjects will be unblinded.

Name of Sponsor/Company: Octapharma Pharmazeutika Produktionsges.m.b.H., [name]			
Name of Investigational Product:	Protocol Identification Code:		
Octagam 10%	GAM10-08 (ProDERM), Version 12		
Name of Active Ingredient:	Date of Protocol:		
Immune Globulin Intravenous, Human 10%	18-Jun-2019		

Subjects originally **randomized to placebo** and switched to 2 g/kg (20 mL/kg) Octagam 10% after confirmed deterioration and who do not further deteriorate during their Octagam 10% treatment will continue and receive 2.0 g/kg (20 mL/kg) Octagam 10% during the 6-months Extension Period. For subjects who will be stable on 2.0 g/kg (20 mL/kg) Octagam 10%, the investigator may decide to switch the subject to 1.0 g/kg (10 mL/kg) Octagam 10%, at Week 28. Subjects originally **randomized to placebo** and switched to Octagam 10% due to confirmed deterioration, who deteriorate also during Octagam 10% treatment at 2 consecutive visits will drop-out after response assessment at Week 16 and will not enter the Extension Period.

Subjects originally **randomized to Octagam 10%** who deteriorate at 2 consecutive visits in the First Period and who were subsequently switched to placebo will drop-out after the response assessment at Week 16 and will not enter the Extension Period.

Subjects dropping out due to confirmed deterioration will in any case be classified as non-responders in the statistical analysis.

Any subject deteriorating in the Extension Period will drop-out, independent of the initially assigned treatment arm.

The study assessments and scheduled time points are summarized in the flowchart following this Study Outline.

Statistical Analysis Plan:

The primary endpoint measure 'response' will be assessed at Week 16 based on the TIS score; a subject is defined as responder if

- (i) the subject has a TIS score of ≥20 points at Week 16 and
- (ii) the subject has not met "Confirmed Deterioration" criteria at 2 consecutive visits as defined in Section 4.3.1 up to (including) Week 16

Otherwise the patient will be counted as a non-responder.

The proportion of responders within both treatment groups will be compared by Cochran-Mantel-Haenszel test, stratified by global disease activity (randomization stratum), using two-sided alpha level of 0.05. The primary analysis will be considered as success if the proportion of responders is significantly higher in the Octagam group compared to the placebo group.

Moreover, an exact two-sided 95% confidence-interval will be constructed for the overall difference in the proportion of responders between Octagam and placebo group, using the 'exact riskdiff' option of the SAS FREQ procedure.

In a sensitivity analysis for the primary endpoint, a logistic regression model will be applied, including global disease activity and further baseline variables as applicable as covariates.

Name of Sponsor/Company: Octapharma Pharmazeutika Produktionsges.m.b.H., [name]			
Name of Investigational Product:	Protocol Identification Code:		
Octagam 10%	GAM10-08 (ProDERM), Version 12		
Name of Active Ingredient:	Date of Protocol:		
Immune Globulin Intravenous, Human 10%	18-Jun-2019		

All other endpoints will be analyzed and presented in full detail by means of descriptive statistics and inferential analyses as appropriate, including summary and frequency tables, confidence intervals and graphs.

A formal statistical analysis plan describing all details of the analyses to be performed will be prepared by the study statistician and approved by the Sponsor.

The evaluation of the primary efficacy endpoint will be based on the intention-to-treat population, i.e. all randomized subjects.

The analysis of safety will be based on the safety analysis set which includes all patients who received at least part of one infusion of Octagam 10% or placebo.

CONFIDENTIAL FLOWCHART OF ASSESSMENTS

 Table 1:
 Flowchart of Assessments Performed During the Study

ASSESSMENTS	Screening	Baseline	line First Period Extension Period				Throughout						
	Visit 1 Week -3 to 0	Visit 2 Week 0	Visit 3 Week 4	Visit 4 Week 8	Visit 5 Week 12	Visit 6 Week 16	Visit 7 Week 20	Visit 8 Week 24	Visit 9 Week 28	Visit 10 Week 32	Visit 11 Week 36	Termination visit Week 40 / Drop-out Visit	Unscheduled Visit
Informed consent	X												
Eligibility criteria	X												
Demographic and baseline characteristics	Х												
Med. hist./Prior medication	X												
Standard ECG	X												
Pregnancy test	X											X	
Blood for viral markers	X											Х	
Blood sample for D-dimers	X												
Randomization		X ²											
Physical examination ²	X		Х			Х			Х			Х	Х
Vital signs³	X	Х	Х	Х	Х	Х	Х	Х	Х	Х	Х		Х
Body weight ²	X					Х			Х				
Safety laboratory ²	X	X	Х	X	Х	Х	Х	Х	Х	Х	X	Х	Х
Serum IgG ²	X	Х	Х	Х	Х	Х	Х	Х	Х	Х	Х	Х	Х
Enzymes ²	X	X	Х	Х	Х	Х			Х			Х	Х
Biomarkers blood sample	X					Х						Х	
Blood sample for additional safety lab ⁵		Х				Х			Х			Х	
Direct Coombs' test⁵		X				X			X			X	
CSM for TIS determination ²	X	X	Х	Х	Х	Х			Х			X	X
CDASI ²		Х	Х	Х	Х	Х			Х			Х	X
SF-36 Health Survey ²		X	_			Х						Х	
Wells score for DVT ⁴	Х	Х	Х	Х	Х	Х	Х	Х	Х	Х	X		Х
Wells score for PE⁴	Х	X	Х	Х	Х	Х	Х	Х	Х	Х	X		Х
Infusion of IMP ¹		X*	X*	X*	X*	X**	X**	X**	X*	X*	Χ#		
Adverse event monitoring		Throughout the study											
Concomitant medication			Throughout the study										

¹ Infusion cycles can last between 2 to 5 days, consisting of 2 or more infusion episodes.

²Before IMP administration;

³ Before, during and after each infusion episode;

⁴ At screening and after each infusion cycle;

⁵ Before and after infusion cycle;

^{*}Blinded infusion of either placebo or 2.0 g/kg Octagam 10%

^{**}Unblinded infusions of 2.0 g/kg Octagam 10%;

[figure not shown]
[#]In case subject is stable on the 2.0 g/kg Octagam 10% dose, they can be switched to 1.0 g/kg Octagam 10%, at the discretion of the investigator

[name]

[name]

PROTOCOL SIGNATURES

This study is intended to be conducted in compliance with the protocol, Good Clinical Practice and applicable regulatory requirements.

Clinical Project Manager Signature Date

Octapharma Pharmazeutika Produktionsges.m.b.H.

[name]

Manager Biometrics

Signature

Date

18 June 2019

Date

Octapharma Pharmazeutika Produktionsges.m.b.H.

Version 12 18-Jun-2019

PROTOCOL SIGNATURES

This study is intended to be conducted in compliance with the protocol, Good Clinical Practice and applicable regulatory requirements.

Signature

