3.1.2 Secondary Endpoints

Efficacy:

- Proportion of TIS responders by improvement category (minimal, moderate, major) at Week 16 and Week 40.
- Mean change from baseline (Week 0) to end of First Period (Week 16) in modified Cutaneous Dermatomyositis Disease Area and Severity Index (CDASI).[29]
- Mean change from end of First Period (Week 16) to end of Extension Period (Week 40) in modified CDASI.
- Mean change from Baseline (Week 0) to end of First Period (Week 16) and Extension Period (Week 40) in:
 - o SF-36v2 Health Survey;
 - o Individual 6 Core Set Measures (CSM) used for TIS calculation.
- Mean TIS from Baseline (Week 0) to end of First Period (Week 16) and from Baseline (Week 0) to end of Extension Period (Week 40).
- Time to minimal, moderate and major improvement in TIS.
- Time to confirmed deterioration in the First Period and overall.
- Proportion of subjects in each treatment arm who met confirmed deterioration criteria up to (including) Week 16

Safety (throughout the entire First and Extension Period):

- Occurrence of all AEs with particular emphasis on thromboembolic events (TEEs) and hemolytic transfusion reactions (HTRs).
- Occurrence of all adverse drug reactions (ADRs) and suspected ADRs.
- Vital signs (blood pressure, heart rate, body temperature and respiratory rate).
- Physical examination (at Screening and every 12 weeks from Week 4 on).
- Laboratory parameters (hematology, clinical chemistry).

Safety (at Baseline and end of Extension Period):

- Tests for viral safety.
- Pregnancy test, if applicable.

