6.1.2 Visit 2 (Week 0; Baseline of First Period)

Subjects who are eligible will visit the study site and enter the controlled phase (First Period) after randomization.

Visit 2 should take place within 3 weeks after the Screening Visit.

All eligible subjects will receive their first infusion of either 2.0 g/kg (20 mL/kg) Octagam 10% or placebo as per randomization. The following assessments will be performed:

Before infusion cycle:

- Randomization and enrollment into the double-blind treatment period.
- SF-36v2.
- Vital signs.
- Blood sample for safety laboratory (hematology and clinical chemistry).
- Blood sample for additional safety lab parameters "Panel 1" (serum haptoglobin and plasma-free hemoglobin)
- Direct Coombs' test (if positive, the antibodies responsible for the positive Coombs' test will be eluted to investigate their specificity (anti-A, anti-B or anti-D)).
- Blood sample for serum IgG.
- Blood samples for enzymes.
- CSM.
- CDASI.

Before, during and after each infusion episode:

- Administration/Infusion of IMP (2.0 g/kg [20 mL/kg] Octagam 10% or placebo given in infusion episodes over 2 to 5 consecutive days).
- Vital signs before, at least once during and at least 1 hour after each infusion episode.

At least 1 hour after the infusion cycle:

- Blood sample for additional safety lab parameters "Panel 2" (serum haptoglobin, hemoglobin, plasma-free hemoglobin, LDH).
- Direct Coombs' test (if positive, the antibodies responsible for the positive Coombs' test will be eluted to investigate their specificity (anti-A, anti-B or anti-D)).
- Wells probability score for DVT. If score is likely for DVT (≥2 points), perform Doppler scan and take blood sample for D-dimers.
- Wells probability score for PE.

In addition, AEs will be monitored and concomitant medications will be documented.

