3.2.1. Primary Target Variables

The evaluation of the primary endpoint will be based on the newly developed Total Improvement Score (TIS), a scale from 0 to 100, with 20-39 points being minimal improvement, 40-59 points being moderate improvement, and ≥ 60 points being major improvement (Aggarwal et al., 2017, please refer to the protocol for details).

In the context of this study, subjects need to have at least minimal improvement at Week 16 (i.e. $TIS \geq 20$) to qualify as responders.

The primary endpoint is defined as the proportion of responders in the 2.0 g/kg Octagam 10% and placebo arms at Week 16, a responder being defined as a subject with an increase from baseline (Week 0) of ≥ 20 points on the Total Improvement Score (TIS) and who has not met "Confirmed Deterioration" criteria at 2 consecutive visits as defined in Section 8.4 up to (including) Week 16.

The TIS is based on the assessment of six core set measures (CSMs):

1. Physician Global Activity: Global Disease Activity (GDA), assessed by the investigator on a Visual Analog Scale (VAS)
2. Patient Global Activity: GDA, assessed by the patient on a VAS
3. Manual muscle testing: MMT-8 Muscle Grading and Testing
4. Health Assessment Questionnaire (HAQ): Standard HAQ used by the International Myositis Assessment and Clinical Studies Group (IMACS)
5. Enzymes: Aldolase, CK, ALAT, ASAT, LDH
6. Extra muscular activity: Evaluated as part of Myositis Disease Activity Assessment Tool [MDAAT]

Please refer to the protocol for further details and references on these CSMs. The CSMs will be assessed at Screening, at each visit of the first period, at Visit 9 (Week 28), and at the Termination Visit.

The TIS is calculated as a sum of sub-scores as detailed below. The level of improvement will always be based on the comparison of the current CSMs compared to the baseline (Week 0) values.

Core set measure	Level of improvement	Level score
Physician Global Activity	Worsening to 5% improvement	0
	>5% to 15% improvement	7,5
	>15% to 25% improvement	15
	>25% to 40% improvement	17,5
	>40% improvement	20
Patient Global Activity	Worsening to 5% improvement	0
	>5% to 15% improvement	2,5
	>15% to 25% improvement	5
	>25% to 40% improvement	7,5
	>40% improvement	10
Manual muscle testing (MMT)	Worsening to 2% improvement	0
	>2% to 10% improvement	10
	>10% to 20% improvement	20
	>20% to 30% improvement	27,5
	>30% improvement	32,5
Health Assessment Questionnaire (HAQ)	Worsening to 5% improvement	0

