3.2.2. Secondary Target Variables

For Efficacy and Quality of Life (QoL), secondary endpoints will be:

- Proportion of TIS responders by improvement category (minimal, moderate, major) at Week 16 and Week 40.
- Mean change from baseline (Week 0) to end of First Period (Week 16) in modified Cutaneous Dermatomyositis Disease Area and Severity Index (CDASI)
- Mean change from end of First Period (Week 16) to end of Extension Period (Week 40) in modified CDASI.
- Mean change from Baseline (Week 0) to end of First Period (Week 16) and Extension Period (Week 40) in:

- SF-36v2 Health Survey;
- Individual 6 Core Set Measures (CSM) used for TIS calculation.
- Mean TIS from Baseline (Week 0) to end of First Period (Week 16) and from Baseline (Week 0) to end of Extension Period (Week 40).
- Time to minimal, moderate and major improvement in TIS.
- Time to confirmed deterioration (defined on basis of the CSM assessments, see section 8.4 for details) in the First Period and overall.
- Proportion of subjects in each treatment arm who met “confirmed deterioration” criteria up to (including) Week 16

For Safety, target variables will be:

- Occurrence of adverse events (AEs) with an emphasis on thromboembolic events (TEEs) and hemolytic transfusion reactions (HTRs)
- Wells probability scores for deep vein thrombosis (DVT) and pulmonary embolism (PE), and Doppler scan (if indicated)
- Occurrence of all adverse drug reactions (ADRs) and suspected ADRs
- Vital signs (blood pressure, heart rate, body temperature and respiratory rate)
- Physical examination (at Screening and every 12 weeks from Week 4 on)
- Laboratory parameters (hematology, clinical chemistry, IgG, enzymes, viral markers, Coombs' test [plus specific antibodies if positive], D-dimers)
- Pregnancy test

4. Study Methods

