10.2. Secondary efficacy endpoints

All secondary efficacy endpoints will be analyzed and presented in full detail by means of descriptive statistics and inferential analyses as appropriate.

For TIS response at Week 16 by improvement category, the proportion of subjects with at least moderate improvement and the proportion of subjects with major improvement will be calculated together with subject counts and the associated 2-sided 95% confidence interval (CI) for the difference in the proportion of patients with improvement. Moreover, both treatment groups will be compared using a Cochran-Mantel Haenszel test, analogously as for the primary endpoint. The proportion of subjects in each treatment arm who meet confirmed deterioration criteria up to (including) Week 16 will be presented in the same way.

All mean changes to be evaluated as secondary endpoints (listed in section 3.2.2) will be presented by a full set of descriptive parameters: number of subjects with non-missing values, mean, standard deviation, median, minimum and maximum, 1st and 3rd quartile, 95% CI. Moreover, for all continuous secondary endpoints, an analysis of covariance (ANCOVA) will be used to analyze changes from baseline to Week 16. For patients who are switched to the alternate treatment before Week 16, the last value prior to switch will be carried forward to Week 16 and used to calculate change from baseline to Week 16. The model will include treatment and global disease activity as a fixed factor. Center will be included as random factor. The baseline value of the variable to be analyzed will be included as a covariate. Least square means will be derived and presented together with 95%-confidence intervals by treatment group. Moreover, two-sided 95% confidence intervals will be derived for the overall difference in least square means between Octagam and placebo treatment. As sensitivity analysis, a modified ANCOVA model will be used, where the changes from baseline to Week 16 are calculated based on Week 16 values, even if a patient is switched to the alternate

treatment before Week 16. To incorporate the switch into the model, the variable crossover (yes/no) which indicates if there was a switch to the alternate treatment will be included as additional factor into the ANCOVA model, as well as the treatment-by-cross-over interaction term.

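### For five of the six core set measures the Week 16 ANCOVA leaves the measure's own Screening value unused; for Physician GDA it enters only as a three-level stratum

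*Protocol*

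**What the plan says.** **Measurement.** Protocol Table 1 marks the row "CSM for TIS determination", and the separate enzymes row, at Screening and at Week 0 before study drug. Protocol 6.1.1 and 6.1.2 list the same assessments. SAP 3.2.1 agrees: "The CSMs will be assessed at Screening, at each visit of the first period". On the gap between the two readings, Protocol 6.1.2 says: "Visit 2 should take place within 3 weeks after the Screening Visit". Randomisation is at Visit 2 (Protocol 6.1.2 and 9.3), so the Screening reading always precedes it.

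**Endpoints.** Protocol 3.1.2 lists as secondary endpoints the changes in "Individual 6 Core Set Measures (CSM) used for TIS calculation". SAP 3.2.2 fixes the reference point: "Mean change from Baseline (Week 0) to end of First Period (Week 16) and Extension Period (Week 40) in" these measures.

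**Model.** SAP 10.2 says that "for all continuous secondary endpoints, an analysis of covariance (ANCOVA) will be used to analyze changes from baseline to Week 16". On covariates it says "The baseline value of the variable to be analyzed will be included as a covariate", and on factors "The model will include treatment and global disease activity as a fixed factor", with centre as a random factor. Protocol 9.2.2 describes the same model. SAP 10.1 identifies global disease activity as the randomisation stratum. SAP 8 and Protocol 9.2 place it at Screening in three levels, and SAP 4.3 derives it from the Physician's GDA in bands 0–3, 4–6 and 7–10.

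**The concern.** Two readings of the same measure are taken before treatment, but for five CSMs only the later one enters the model. VAS scores, MMT-8 and HAQ can be expected to vary from visit to visit, so two readings may predict Week 16 better than one. A better predictor measured before randomisation reduces residual variance and narrows the confidence interval for the treatment difference, without bias.

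The Screening values should be nearly complete, because inclusion criterion 4 is judged on the CSMs. The trial is in a rare disease with about 55 sites, and withdrawals are not replaced, so precision that needs no further subjects is worth considering. At stake is the width of the intervals for the six CSM changes, and nothing in the primary analysis.

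**Working it through.** **1. The plan's own figure.** The documents give no precision or power for any CSM comparison. The only sample size is for the primary endpoint: 0.6 against 0.3, two-sided 0.05, 80% power (Protocol 9.1, SAP 6).

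n per arm = [1.96·√(2·0.45·0.55) + 0.8416·√(0.6·0.4 + 0.3·0.7)]² / 0.3² = (1.379 + 0.565)² / 0.09 ≈ 42

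This gives 84 in total (power 80.03%) and reproduces the stated figure. At 94 subjects the power is 84.4%. Neither number depends on the ANCOVA.

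**2. Formula for the gain.** Write p = corr(Screening, Week 0), a = corr(Week 0, Week 16) and b = corr(Screening, Week 16), within arm. With Week 0 as a free covariate, residual variance (as a fraction) is the same for the Week 16 value and for change from Week 0:

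- Week 0 only: 1 − a²
- both readings: 1 − (a² + b² − 2pab)/(1 − p²)

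The formula ignores the stratum and centre. All correlations below are assumptions.

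| p | a | b | Variance ratio, both vs Week 0 only | Reduction |
|---|---|---|---|---|
| 0.5 | 0.5 | 0.5 | 0.889 | 11.1% |
| 0.6 | 0.6 | 0.6 | 0.859 | 14.1% |
| 0.7 | 0.7 | 0.7 | 0.830 | 17.0% |
| 0.8 | 0.8 | 0.8 | 0.802 | 19.8% |
| 0.7 | 0.6 | 0.6 | 0.901 | 9.9% |
| 0.8 | 0.6 | 0.6 | 0.937 | 6.3% |
| 0.7 | 0.5 | 0.5 | 0.941 | 5.9% |
| 0.8 | 0.5 | 0.5 | 0.963 | 3.7% |
| 0.9 | 0.6 | 0.6 | 0.970 | 3.0% |
| 0.9 | 0.5 | 0.5 | 0.982 | 1.8% |
| 0.8 | 0.6 | 0.55 | 0.979 | 2.1% |
| 0.8 | 0.6 | 0.50 | 0.998 | 0.2% |
| 0.8 | 0.6 | 0.48 | 1.000 | 0% |

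Example, row 6: 1 − 2·0.36/1.8 = 0.600, and 0.600/0.640 = 0.937. The last row is serial decay (b = p·a), where Week 0 carries everything Screening knows. In the unequal rows a ratio of 0.963 to 0.901 is worth 94/0.963 ≈ 98 to 94/0.901 ≈ 104 subjects.

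**3. Cost if Screening adds nothing.** One degree of freedom. With about 86 residual degrees of freedom before and 85 after, 86/85 = 1.012, a loss of about 1% of variance.

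**4. Physician GDA.** Its Screening value is already present in three bands. This was simulated with 1,000,000 draws, an assumed Screening VAS with mean 5.5 and SD 1.8, and cuts at 3.5 and 6.5. The (p, a = b) pairs were (0.5, 0.5), (0.7, 0.7), (0.8, 0.8), (0.7, 0.5), (0.8, 0.6) and (0.9, 0.6). The stratum alone captured 40–72% of the available gain. Adding the continuous Screening value cut residual variance by a further 1.8–9.8%.

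**5. The mean of the two readings as the only covariate.** This looks simpler but is harmful when the outcome stays change from Week 0. With all correlations 0.6:

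- Var(change) = 2 − 1.2 = 0.8
- Cov(change, mean) = 0.6 − 0.8 = −0.2
- Var(mean) = 0.8
- residual = 0.8 − 0.04/0.8 = 0.75, against 0.64 for the planned model

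Across the four equal-correlation cases and the pairs (p, a = b) = (0.7, 0.6), (0.8, 0.6), (0.7, 0.5) and (0.8, 0.5), variance rises by 8–22%.

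**The case against.** A reader might infer that the model adjusts for Week 0 alone in all six comparisons, and that precision is certainly being lost. The documents do not support either inference. The Screening GDA stratum is a fixed factor in every ANCOVA, and in the Physician GDA model it is a banded form of that endpoint's own Screening value. The gain itself depends on correlations that the documents do not give.

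The larger gains also need favourable assumptions. Most rows above let Screening predict Week 16 as well as Week 0 does, although it is up to three weeks older. Lowering b from 0.60 to 0.55 (p = 0.8, a = 0.6) cuts the reduction from 6.3% to 2.1%. The 11–20% range requires readings at most three weeks apart to correlate no better than readings 16 weeks apart across treatment.

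There are document-based reasons to expect Screening to be the weaker predictor. Washouts run up to randomisation, not Screening (Protocol 4.2.1, 4.2.2 and Table 5), so some subjects may still be washing out at Screening. Screening MMT-8 is also truncated by the entry limit of 142.

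Finally, a single-baseline ANCOVA is valid and unbiased, and Week 0 is the consistent reference for the TIS, confirmed deterioration and the change endpoints. All of this stands. It makes the point an option rather than a correction, and leaves intact that five Screening values are collected and not used.

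**Conclusion.** The point holds as a modest, optional improvement. Each CSM's Screening value is available before randomisation. It is unused for five measures and used only in three bands for Physician GDA. Under assumed correlations, adding it lowers residual variance by about 0–10%. The lower part of that range is more realistic if Screening predicts Week 16 somewhat less well than Week 0. The 11–20% range belongs only to the case where all three correlations are equal at 0.5–0.8. Physician GDA gains less than the same correlations would give without the stratum. The worst case is about 1% of variance.

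It would be wrong to read this as an error, a bias or a threat to the trial's conclusion. The primary CMH test, the TIS and the sample size of 84 (94 enrolled) are unaffected. No CSM comparison has a stated power, so a gain expressed in power would be hypothetical. The point cannot extend to CDASI or SF-36v2, which are not measured at Screening.

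**What to change.** In SAP 10.2 and Protocol 9.2.2, before unblinding, add one sentence for the six CSM endpoints: the Screening value of the analysed measure enters as a second, separate continuous covariate alongside the Week 0 value, with change still measured from Week 0.

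- Do not replace the two values by their mean as a single covariate.
- For enzymes, use the Screening value of the enzyme selected as most abnormal at Week 0 (SAP 3.2.1).
- State how a missing Screening value is handled, so that no subject drops out of the model because of it.
- Leave CDASI and SF-36v2 as planned.

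The cost is a sentence or two of text and one degree of freedom per model, with no new data, visit or burden on subjects. The timing matters, because SAP 2 and 5.1 require analyses not identified in the plan to be reported as unplanned.
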